- Number of Adverse Events of special interest (Ischemia and/or necrosis of finger(s) or toe(s), documented bowel ischemia, occurrence or worsening of acute renal failure with need of renal replacement therapy, need of tracheal intubation in a patient previously not intubated, Cardiac arrest, nerve injury of upper limb(s), skin lesions at cuff location or at IAC insertion site, arterial thrombosis, hematoma, arterial pseudo aneurysm, haemorrhage at IAC insertion site either during IAC placement or later)
- Incremental Cost-Effectiveness Ratio (ICER): «Cost/Life day gained at 28 days», from the health system viewpoint, between the non invasive strategy and the recommended invasive strategy: $(\text{Costs}_{\text{NIBP}} - \text{Costs}_{\text{IAC}}) / (\text{Life expectancy at D28}_{\text{NIBP}} - \text{Life expectancy at D28}_{\text{IAC}})$
- Budget impact analysis of the generalization of the non-invasive strategy (in case of demonstrated non inferiority) in France from the viewpoint of the French health system on a 5 years' time frame
- Patient-reported pain and discomfort related to the device used for BP monitoring will be assessed using numerical scales in both groups, once a day as soon as the patients are awakened and capable of correctly evaluating their pain and discomfort (cf. APPENDIX 1)

3. Interventions

Once included, the patient will be randomly assigned, for the 28 following days, to one of the following strategies:

a) **“usual care”**: An IAC will be inserted as soon as possible (within the first four hours after randomization)

and will be maintained except in case of IAC futility (as defined below), suspected or proven IAC related infection or thrombosis (at discretion of attending physician) until day 28 or ICU discharge (whichever comes first). After day 28, clinicians may choose to maintain or to remove IAC.

During the intervention period, in case of removal for accidental or other reasons than futility (i.e. IAC infection, IAC dysfunction, unavailability to draw blood), another IAC should be inserted during the next four hours (insertion site at the discretion of the attending physician).

In case of IAC removal for other futility criteria than decision of palliative care, an IAC will be inserted within the four hours of new onset of circulatory failure as defined below:

- Presence of
 - Persisting hypotension (systolic blood pressure less than 90 mmHg or mean arterial blood pressure less than 65 mmHg) for more than 4 hours

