4.5. Study outline

4.6. Schedules of procedures for each enrolled patient

	Inclusion	Short-term follow up until D28 or discharge from ICU (whichever comes first)			Long-term follow up
Study Day 1 starts once patient is randomized		D1, D2, D3	D4, D5, D6, D7	D8 to D28	D90
Inclusion/exclusion criteria	X				
Informed consent	X				
Randomisation	X				
Delayed pursuit consent if applicable		X	X	X	X
Clinical assessment (heart rate, blood pressure, SpO ₂ , pain assessed during transcutaneous vascular puncture ^{a,e} , fluid balance ^b)		X	X	X	
Catheter evaluation (IAC insertion, IAC removal, catheter-related infection)		X	X	X	
Laboratory sampling status (blood volume draw, number of attempts at arterial puncture)		X	X	X	
Therapeutic assessment (number of packs of red blood cells transfused)		X	X	X	
Supportive therapy assessment (respiratory status, ventilator settings ^c , renal replacement therapy ^c , vasopressor support ^b)					
Census evaluation (survival status, in ICU, in Hospital)		X	X	X	X
Specific laboratory testing for the study (SOFA)		X	X		
Blood haemoglobin ^d		X	X	X	
Number of arterial and venous punctures for lab tests, arterial catheter insertion and set up of monitor, blood drawings from arterial catheter or other vascular line, through ICU stay ^e		X	X	X	
Microcosting of staff time and equipment used for arterial and venous punctures for lab tests, arterial catheter insertion and set up of monitor, blood drawings from arterial catheter or other vascular line, through ICU stay ^e		X			
Adverse events/Serious adverse events ^f		X	X	X	X
Query on the French National Hospital Discharge Database (at the end of the study)		X	X	X	

^a: assess by visual or numeric scale for patients able to communicate and by Behavioural Pain Scale(66) otherwise

^b: fluid balance will be assessed only from D1 to D7

^c: if applicable

^d: if available

^e: on a 10% random sample of study population

^f: Collection and reporting of adverse events will begin once the informed consent is signed

Patients' follow-up:

Patients will be examined for signs of shock and organ failures throughout their ICU stay, as done in routine practice.

Their deceased/alive status will be recorded at ICU discharge, hospital discharge, by day 28 and by day 90

Lost-to-follow-up

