The primary analysis of the primary outcome will be the determination of the between-group difference (noninvasive group minus invasive group) in rates of day-28 mortality, estimated with a binomial generalized estimating equation (GEE) model with identity link adjusted on the stratification variables and on the center effect (Pedroza 10.1186/s12874-016-0217-0). A switch from noninferiority to superiority is *a priori* planned if the hypothesis of noninferiority with a noninferiority margin of 5 percentage points is verified. These hypotheses will be assessed using the stratified Farrington-Manning test for differences in proportions.

Secondary outcomes analysis

Statistical analyses for secondary outcomes will not be adjusted for multiplicity; therefore, secondary-outcome findings should be interpreted as exploratory.

- Day-90 mortality will be analyzed with the same model as the primary outcome .
- Cumulative incidence of death from randomization through Day 90 will be analyzed with a Cox model.
- ICU mortality and hospital mortality will be analyzed in a competing risks framework. A hazard ratio will be computed from the whole groups using a Fine and Gray regression model. ICU discharge or hospital discharge will be considered as competing events.

The following outcomes will be described with median and quartiles and compared between groups using median differences:

- Duration of ICU stay from randomization to discharge.
- Duration of hospital stay from randomization to discharge.
- Duration of mechanical ventilation from randomization and Day 28.
- Ventilator-free days from randomization to Day 28.
- Renal replacement therapy-free days from randomization to Day 28.
- Vasopressor therapy-free days from randomization to Day 28.

For each outcome, 95% confidence intervals of the median difference will be computed using unstratified bootstrapping (10,000 samples with replacement). Vasopressor therapy-free days, renal replacement therapy-free days and duration of mechanical ventilation do not account for the competing risk of death.

The following outcomes will be represented with boxplots at each day:

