- Evolution of daily SOFA score during the first seven days after randomization. This outcome will be analyzed with a linear mixed model with time (considered as a quantitative variable) and the intervention group as fixed effects, an interaction term between group and time, and a random effect on the patient. The regression terms will be estimated with their 95% confidence intervals, with the noninvasive group as the reference. The same model will also be analyzed with time considered as a qualitative variable in the aim to describe the mean difference between groups at each time, using contrasts.
- Mean daily blood volume drawn for laboratory testing during ICU stay.
- Evolution of blood hemoglobin level from randomization to Day 28.
- Evolution of hematocrit from randomization to Day 28.
- Daily amount of intravenous fluid given for rapid vascular volume expansion during the first seven days after randomization.
- Daily fluid balance during the first seven days after randomization.

The following outcomes will be analyzed with a difference of proportions:

- Proportion of patients treated by renal-replacement therapy between randomization and Day 28.
- Proportion of patients treated by vasopressor between randomization and Day 28.

The time free of arterial catheter insertion, from randomization through Day 90 will be graphically represented with cumulative incidence curves.

The following outcomes will be analyzed with the use of a quasi-Poisson regression model and expressed as rate ratios, with the duration of stay in the ICU as the offset:

- Number of arterial and central venous catheter insertion during ICU stay from randomization to Day 28.
- Number of blood cultures performed during ICU stay from randomization to Day 28.
- Number of blood draws from the venous catheter during ICU stay from randomization to Day 28.
- Number of attempts at arterial puncture during ICU stay from randomization to Day 28.
- Number of red blood cell packs transfused during ICU stay from randomization to Day 28.
- Numbers of arterial and central venous catheter-related bloodstream infections during ICU stay from randomization to Day 28.

Safety outcomes and analyses

- The number of adverse events of special interest will be described in each group and compared using a chi-squared test.

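### As written, the quasi-Poisson models count events only to Day 28 but give the ICU-stay offset no Day-28 limit, so the rate ratios shift if the arms differ in ICU time after Day 28

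*SAP*

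**What the plan says.** In the SAP, Secondary outcomes analysis, six outcomes share one quasi-Poisson model that yields rate ratios, and its exposure term is given as "with the duration of stay in the ICU as the offset". They are catheter insertions, blood cultures, draws from the venous catheter, arterial puncture attempts, red cell packs and catheter-related bloodstream infections. All six carry the same count window, for example "Number of blood cultures performed during ICU stay from randomization to Day 28" and "Number of red blood cell packs transfused during ICU stay from randomization to Day 28".

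The offset sentence gives no window. The only place where the SAP defines the length of ICU stay is the list of median-difference outcomes: "Duration of ICU stay from randomization to discharge". That same list does limit another duration: "Duration of mechanical ventilation from randomization and Day 28". The SAP's Further clarifications do not mention the offset.

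The protocol foresees ICU stays longer than 28 days. In section 3 (Interventions) the usual-care catheter is kept "until day 28 or ICU discharge (whichever comes first). After day 28, clinicians may choose to maintain or to remove IAC". The schedule in section 4.6 ends daily data collection at the same point: "Short-term follow up until D28 or discharge from ICU (whichever comes first").

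Protocol section 6.2 also used ICU stay as the offset, in negative binomial models. In section 2.3, blood cultures, arterial puncture attempts and catheter insertions were counted over the whole ICU stay, which matched that offset. Red cell packs were already limited to Day 28. The SAP now limits all six counts to Day 28 and leaves the offset wording without a limit.

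The SAP's safety section uses the same offset for days with pain or discomfort.

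**The concern.** An offset should measure the time during which the counted events could occur. A patient who stays 60 days in the ICU can contribute events from at most 28 of them, yet on the written definition contributes 60 days of exposure. If ICU time after Day 28 differs between arms, by treatment effect or by chance, that difference enters the rate ratios for punctures, blood draws, transfusions and infections, although it says nothing about how often those events occurred in the observed window.

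These models carry much of the evidence for the protocol's expected benefits (section 5: less blood drawn, less transfusion, fewer catheter infections). The SAP drops three other infection outcomes for lack of reliable data, so catheter-related bloodstream infection is the infection rate that remains.

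**Working it through.** The documents state no rate, rate ratio or ICU-stay distribution, so there is no figure of the plan to reproduce on this point.

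**Inputs from the documents.** Counts: ICU days from randomisation to Day 28. Offset: ICU stay, no limit stated, defined elsewhere as randomisation to discharge. Effect measure: rate ratio. Scale: 1010 planned patients, 505 per arm (protocol section 6.1).

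**Algebra.** The SAP lists no covariates for these models, so I take group as the only term. With a log link, the fitted rate in an arm is total counts divided by total offset time. Let L be a patient's full ICU stay and T = min(L, 28). Then

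- counts / ΣL = (counts / ΣT) × f, where f = ΣT / ΣL;
- rate ratio (full-stay offset) = rate ratio (capped offset) × f(noninvasive) / f(invasive).

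This is an identity. If the two f values are equal, the multiplier is exactly 1. If one arm has more ICU time after Day 28, its f is smaller and its rate looks lower than it was.

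**Hand example (assumed values).** Patients who leave by Day 28 stay 8 days on average. A share p stays longer, by 20 days on average.

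- p = 5%: ΣT per patient = 0.95×8 + 0.05×28 = 9.0; ΣL = 9.0 + 0.05×20 = 10.0; f = 0.900.
- p = 10%: ΣT = 0.90×8 + 0.10×28 = 10.0; ΣL = 10.0 + 0.10×20 = 12.0; f = 0.833.
- Noninvasive 5%, invasive 10%: 0.900/0.833 = 1.08. Arms reversed: 0.833/0.900 = 0.926. Both at 10%: 1.000.

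**Lognormal stays (assumed).** With log-mean μ and log-SD s, E[L] = exp(μ + s²/2) and E[T] = E[L]·Φ((ln 28 − μ − s²)/s) + 28·[1 − Φ((ln 28 − μ)/s)], so f = E[T]/E[L]. For 8% of noninvasive and 10.5% of invasive patients beyond Day 28:

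| How the arms differ | f noninvasive | f invasive | Multiplier |
|---|---|---|---|
| Median only, log-SD 0.9 | 0.882 | 0.855 | 1.03 |
| Median only, log-SD 1.3 | 0.755 | 0.712 | 1.06 |
| Spread only, median 8 days | 0.884 | 0.823 | 1.07 |
| Spread only, median 6 days | 0.826 | 0.740 | 1.12 |

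The range is 1.03 to 1.12. Reversed, it is 1/1.12 to 1/1.03, or 0.89 to 0.97. A larger imbalance, 8% against 13%, gives about 1.06 to 1.28 over the same set of assumptions.

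**Check with a fitted model.** Quasi-Poisson fits to 300 simulated trials of 505 per arm, with lognormal stays and a true ratio of 1:

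- 6.1% against 10.6% beyond Day 28: mean ratio 1.07 with the full-stay offset, 1.00 with the capped offset.
- Equal distributions: 1.01 with either offset.

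**Chance imbalance.** With identical true distributions (median 6 to 10 days, log-SD 0.9 to 1.3), f(noninvasive)/f(invasive) still varies from trial to trial. The SD of its log is about 0.035 to 0.11. For comparison, if counts run at 0.2 per day with gamma frailty of variance 1, the correctly capped log rate ratio has a sampling SD of about 0.09 to 0.10. At the low end of the range, the full-stay offset raises it only from 0.097 to 0.104.

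**Absolute rates, if any were reported from this offset.** Over the same assumptions f runs from 0.93 (4% beyond Day 28) to 0.56 (21% beyond Day 28, mean stay 23 days), so rates would be 7% to 44% too low. The upper end is an extreme corner.

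**The case against.** The SAP never says that the offset runs to discharge. That definition belongs to a separate outcome, and the offset sentence stands directly above six outcomes that all end at Day 28. An analyst could read the exposure as ICU days within that window, and daily data collection stops there anyway. The program may therefore already use the capped time. This stands in part: the Day-28 limit is unstated rather than expressly excluded. But the SAP's only definition of ICU stay is uncapped, and the SAP writes a Day-28 limit on ventilation duration where it wants one, so the text taken at its word produces the mismatch.

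A reader might go further and infer that the rates are all too low, or that the trial's rate ratios are wrong or lean towards one strategy. The documents do not support that. The planned output is rate ratios, and the SAP plans no absolute rates from these models. The ratios are untouched when both arms have the same share of ICU time after Day 28. Nothing in the documents says which arm, if either, has more late ICU time, so the direction is open.

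The SAP also labels its secondary findings exploratory and makes no multiplicity adjustment. That limits the weight of the point but does not remove it.

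**Conclusion.** The point holds as a defect of the written plan: the count window and the exposure window do not match for six secondary outcomes. Its effect on a rate ratio depends on between-arm differences in ICU time after Day 28. It is nil for equal shares. Under assumed lognormal stays, it is about 1.03 to 1.12 (or the reciprocal) for 8% against 10.5% of patients beyond Day 28. Chance imbalance adds noise that is small for short-tailed stays and comparable to ordinary sampling error only for heavy-tailed ones. All these sizes rest on assumed ICU-stay distributions and are illustrative. The mechanism does not depend on them.

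The day-28 mortality analysis and the noninferiority conclusion are unaffected. The plan should be corrected because the results concerned bear on the expected morbidity benefit, but nothing here shows that a reported estimate is wrong.

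**What to change.** State in the SAP that, for the six outcomes counted to Day 28, the offset is log(ICU days from randomisation to the earliest of ICU discharge, death or Day 28). Use the same capped offset for the pain and discomfort days model. The SAP gives that count no window of its own, but the protocol's schedule ends daily follow-up at Day 28 or ICU discharge.

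The cost is one sentence and one derived variable from dates already collected. If the program already caps the exposure, the sentence records what was done. If it does not, these models should be re-run with the capped offset. I see no downside: the simulated ratio with the capped offset was 1.00 to 1.01 in every scenario tried when the true ratio was 1.

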- Renal replacement therapy-free days from Day 1 to Day 28 (for this purpose days without renal replacement therapy from Day 1 to Day 28 for survivors at Day 28, and from Day 1 to the date of death for patients dying before Day 28, will be taken into account)
- Proportion of patients treated by vasopressor between Day 1 and Day 28
- Vasopressor therapy-free days from Day 1 to Day 28 (for this purpose days without vasopressor therapy from Day 1 to Day 28 for survivors at Day 28, and from Day 1 to the date of death for patients dying before Day 28, will be taken into account)
- Mean daily blood volume drawn for lab testing during ICU stay
- Number of blood cultures performed during ICU stay
- Number of attempts at arterial puncture during ICU stay
- Evolution of blood haemoglobin level from Day 1 to Day 28
- Evolution of haematocrit from Day 1 to Day 28
- Number of red blood cell packs transfused from Day 1 to Day 28
- Number of transcutaneous arterial and venous puncture for lab tests, arterial catheter insertion and set up of monitor, blood drawing from the arterial catheter or other vascular line through ICU stay and time (min) spent by nurses and physicians (min) on these tasks during the first three days of the

ICU stay (in a random sample representing 10% of the total number of included patients).

- Number of arterial and central venous catheter insertion during ICU stay
- Numbers of arterial and central venous catheter-related infections during ICU stay, expressed as the incidence of new cases per 1000 catheter-days, including local and catheter-related bloodstream infections as consensually defined.(58,59)
- Numbers of local infections of arterial and central venous during ICU stay (number of new cases per 1000 catheter-days).
- Numbers of arterial and central venous catheter-related bloodstream infections during ICU stay, (number of new cases per 1000 catheter-days).
- Number of bloodstream infections during ICU stay, catheter-related or not
- Duration of ICU stay
- Duration of hospital stay
- ICU mortality
- Hospital mortality
- Day-90 mortality

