3.1. Differences between the usual care and the non-invasive care strategies

Description of blood pressure monitoring among randomisation group

In the “usual care” group, BP will be monitored through the arterial line sensor connected to the usual monitoring device (fluid-filled system). Site of IAC insertion, insertion technique, skin antisepsis and catheter care will be at the discretion of the attending physician, according to local guidelines. Non-invasive BP monitoring is not allowed, except when IAC is considered futile (as defined above) and during IAC insertion or replacement.

In the “non-invasive” group, automated oscillometric monitor will be used to monitor BP. ***The size of the cuff will be adapted according of the arm circumference and manufacturer recommendations.*** The dedicated indicator will be placed at the level of the artery. If deemed appropriate according to clinical context, the cuff may be placed at the lower limb.(30)

In both groups, alarm thresholds and interval of BP measurements will be left at the discretion of the attending physician.

Blood sampling technique

In the “usual care” group, blood samples for lab tests will be drawn from the IAC, as many times as

necessary. Blood-drawing through the central venous catheter is forbidden, excepted for ScvO₂ measurements.

In the “non-invasive” group, blood-drawing through the central venous catheter is recommended for usual lab tests. To avoid interruption or bolus on specific continuous therapeutics, we strongly recommend infusing vasopressor agents in a dedicated line of the central venous catheter that should not be the line used for sampling. Regarding the monitoring of ventilation parameters and of the lactate blood level, we encourage the attending intensivists and investigators to rely on SpO₂ (60,61) to assess oxygenation, and on predicted pH, PaCO₂, and lactate derived from central venous blood analysis.(47) For this purpose, formula to derive estimates of arterial blood parameters and abacuses giving probabilities of true arterial values below or above given thresholds for each predicted value will be provided to the sites (APPENDIX 2).

Arterial blood gas parameters

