We will develop a mobile application to automatically estimate arterial blood gas parameters from central venous parameters and SpO₂ (see APPENDIX 2). As the study is not cluster randomized, the mobile app with the arterial blood parameters calculator will be available for all investigators regardless whether they are in charge of patients randomized in the “invasive” (presence of IAC) or the non-invasive group. To minimize this potential source of bias, we want to emphasise, and this will be clearly reminded in the mobile app, that central venous blood drawing will not be allowed in the “invasive” group, except for ScvO₂ measurements.

Modalities of patients' general management

In both group, patients will be managed following international and national guidelines, except for the IAC insertion.

Regarding blood sampling for lab tests, to avoid unnecessary blood spoliation in both arms, we strongly encourage investigators and attending intensivists to properly assess the real need of each lab test ordered. We discourage sampling for routine (daily or more frequent) monitoring or after changes in FiO₂ or PEEP. If blood gas were drawn for suspicion of metabolic or respiratory disorder, only the control after therapeutic intervention will be allowed.

In addition, to decrease blood spoliation during sampling through any vascular catheter (IAC for the invasive group, CVC for the non invasive group), we strongly suggest to apply the following procedure that may help minimizing the discard volume of blood withdrawn before the sampling.(62,63)

After cleaning the catheter hub, draw off 3 mL (for sampling through IAC) or 5 mL (through CVC) of blood (i.e., at least 2 times the catheter's priming volume)(64) with a syringe and waste the syringe. Draw the blood sample through the Vacutainer system. Be sure to sample blood from a line of the catheter not dedicated to continuous vasopressor therapy (to avoid bolus or discontinuous infusion).

4. Study design

The projected study will be a multi-centre, pragmatic, randomised, controlled, open, two-parallel-group, non-inferiority clinical trial with 1:1 assignment of interventions.

Although blinding is not possible due to the nature of the assessed intervention, the primary endpoint is objective (mortality at day 28). The trial will associate medical, surgical, and mixed ICUs, as well as academic tertiary care hospitals and community hospitals.

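### The rate ratio for venous-catheter blood draws compares a route that is recommended in one arm and forbidden (except for ScvO2) in the other, while the measure covering all routes, daily blood volume, is given boxplots only

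*SAP*

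**What the plan says.** **SAP, Secondary outcomes analysis.** One listed outcome is the "Number of blood draws from the venous catheter during ICU stay from randomization to Day 28". Each count in that list is compared between arms by a quasi-Poisson rate ratio, offset by length of ICU stay. The same list holds attempts at arterial puncture and blood cultures, but no count of draws from the arterial catheter. Mean daily blood volume appears in a separate list of outcomes to be shown as daily boxplots. In that list a model is written out for the SOFA score only.

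**Protocol 3.1, Blood sampling technique.** In the invasive (usual care) arm, "blood samples for lab tests will be drawn from the IAC, as many times as" the need arises. For that arm the section adds that "Blood-drawing through the central venous catheter is forbidden", with ScvO2 measurement as the exception. The paragraph on the mobile application repeats that "central venous blood drawing will not be allowed in the “invasive” group", with the same exception. In the noninvasive arm, "blood-drawing through the central venous catheter is recommended for usual lab tests".

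**Protocol 2.3 and 4.6.** The protocol outcome covers punctures and "blood drawing from the arterial catheter or other vascular line through ICU stay". The schedule has a matching row, "blood drawings from arterial catheter or other vascular line, through ICU stay", with a footnote limiting it to a 10% random sample.

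**Protocol 6.2, secondary clinical outcomes.** Mean daily blood volume is among the outcomes whose intervention effect is to be estimated with 95% CI from mixed linear models.

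**SAP, Missing analyses and secondary outcomes.** Peripheral venous punctures are listed as not analysable for lack of reliable data. Arterial-catheter draws are not mentioned.

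**The concern.** A between-group rate ratio is informative when the same thing could be counted in either arm. Here the counted route is the recommended one in the noninvasive arm and, apart from ScvO2, a protocol deviation in the invasive arm. The ratio therefore says more about whether sites followed the sampling instructions than about how much blood sampling each strategy generates.

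No other count redresses this. The invasive arm's main route, the arterial catheter, is not counted. The other sampling route with its own rate ratio, arterial puncture, also leans towards the noninvasive arm, where protocol section 3 allows direct puncture as often as indicated.

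What is at stake is the trial's evidence on sampling burden. Secondary objective 2 asks about laboratory testing and its consequences, and the protocol's expected results include less blood drawn for tests. A ratio well above 1 for venous-catheter draws, with only boxplots for blood volume beside it, could be read as more sampling under the noninvasive strategy when the data show nothing of the kind.

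**Working it through.** The documents give no draw rate, rate ratio or power for this outcome, so there is no stated figure to reproduce. The check is how the venous-only ratio relates to the ratio of total sampling.

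**Step 1. Notation.**
- R: ratio of total draws per ICU-day, noninvasive to invasive.
- s: share of invasive-arm draws taken through the venous catheter (ScvO2 draws and deviations).
- c: the same share in the noninvasive arm while no arterial catheter is in place.
- x: share of noninvasive-arm ICU time with an arterial catheter. Protocol section 3 has such patients managed as usual care, so share s is applied to that time.

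**Step 2. Formula.** Per unit of invasive-arm sampling, venous-catheter draws are s in the invasive arm and R × [(1 − x)c + xs] in the noninvasive arm. So

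venous-only rate ratio = R × [(1 − x)c + xs] / s.

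**Step 3. What follows without any numbers.** The factor multiplying R exceeds 1 whenever c > s and x < 1. The two sampling instructions are written to make c larger than s. The venous-only ratio is then above R, and R cannot be recovered unless the shares are known.

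**Step 4. Illustration.** These ranges are assumptions and are not in the documents: s = 0.05 to 0.30, c = 0.5 to 0.8, x = 0 to 0.30.

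| Total sampling | Low end (s = 0.30, c = 0.5, x = 0.30) | High end (s = 0.05, c = 0.8, x = 0) |
|---|---|---|
| Equal, R = 1.0 | (0.7 × 0.5 + 0.3 × 0.3) / 0.30 = 0.44 / 0.30 = 1.47 | 0.8 / 0.05 = 16 |
| 30% lower, R = 0.7 | 0.7 × 1.47 = 1.03 | 0.7 × 16 = 11.2 |

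A count over all routes would return R itself, 1.0 or 0.7. The width of these ranges shows that the documents fix neither the size of the distortion nor the value the ratio will take.

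**Step 5. What the SAP keeps for total sampling.** Mean daily blood volume covers every route. In the schedule (protocol 4.6) it sits in the laboratory sampling row, which does not carry the 10% footnote, so it is not restricted to that sample. The protocol planned a between-group estimate for it. The SAP states none, and its summary of changes does not mention a removal. By contrast, the row with arterial-catheter draws covers about 10% × 1010 = 101 patients.

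**The case against.** The strongest reply is that sampling is not left unmeasured. Blood volume is kept, does not depend on route, is not confined to the subsample, and matches the benefit the protocol expects, which is a smaller amount of blood drawn. That stands, and a reader who inferred that the SAP has no measure of overall sampling would be wrong. It does not repair the venous-only ratio, however, and the SAP gives volume no between-group estimate.

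Second, the ratio is not wholly fixed by allocation. ScvO2 draws are allowed in the invasive arm. Deviations, time after an arterial catheter is removed, and later arterial catheterisation in the noninvasive arm all contribute. The SAP also does not define the venous catheter, whereas the ban concerns the central one. This stands, and is why the claim is that the ratio is largely, not entirely, determined by strategy.

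Third, the ratio could be read as a description of process. The protocol rules out testing the number of patients who received an arterial catheter, but it also plans a model for the number of catheter insertions, so it sets no general rule against comparing outcomes that depend on strategy. This is fair, but counts per arm would serve the descriptive purpose without inviting a wrong inference about total sampling.

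Fourth, secondary objective 2 concerns tests ordered, and one draw can serve several tests. That is correct: no draw count, including a total, measures tests ordered.

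Finally, the SAP labels secondary outcomes exploratory. That limits the consequence, but the label concerns multiplicity and does not make the two arms comparable on this count.

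**Conclusion.** The concern holds in a limited form. The rate ratio for venous-catheter draws is largely determined by the allocated strategy and can exceed 1 when total sampling is equal or lower. This rests on reading the venous catheter as the central venous catheter and on sites broadly following the sampling instructions. Arterial-catheter draws have dropped out of the analysis without being declared, and the measure best able to compare sampling has lost its stated model.

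A reader might go further and infer that the SAP will report a large excess, with the direction of effect reversed. The documents do not support that. They contain no draw rates, the 1.5 to 16 range comes from assumed shares, and its counterpart under a 30% reduction comes down to 1.03.

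The outcome is secondary and exploratory, and the day-28 mortality conclusion is untouched.

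**What to change.** 1. Report venous-catheter draws per arm descriptively, without a rate ratio, and state which venous catheter is meant. Set beside them the arterial-catheter draws from the 10% sample, if these were reliably recorded.
2. Make mean daily blood volume the between-group comparison of sampling, using the mixed linear model with 95% CI already planned in protocol 6.2. State whether the volume includes discarded blood, because protocol 3.1 suggests discarding 3 mL through the arterial catheter and 5 mL through the central venous catheter.
3. If arterial-catheter counts are unusable, add them to the SAP's list of outcomes that cannot be analysed, with the reason.

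A total-draws count is not a safe substitute. Peripheral venous punctures are declared unreliable, and patients without an arterial catheter may need them more often, so a total that omits them could undercount the noninvasive arm. It should not be presented as an unbiased total.

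The cost is SAP wording and slightly more analysis work. The volume comparison needs no new collection if the scheduled data were recorded, and it restores a model already planned in the protocol. Item 1 depends on whether the subsample counts, about 101 patients, are usable.
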